**Table 2 . Study Outcomes, Measures and co-variates**

Efficacy Outcomes		
LDCT order for LCS	6 mo	Survey and EMR
Receipt of LDCT for LCS	6 mo	Survey &EMR
Pt and PCP LCS discussion	6 mo	
Pt perceived risks, benefit, barriers, and self-efficacy using LCS health belief mode 	Baseline & 6 mo	Survey
Process Evaluation Outcomes		
Rate of concordance of EMR and self-report smoking hx	Baseline	Survey& EMR
Showing up to PCP visit	6 mo	
Self-referral to PAF	6 mo	Survey
Pt and provider experience with intervention components	6 mo	Survey& interview
Provider perceived barriers and knowledge of LCS	Beginning 9 mo after first pt enrollment	Survey
Covariates		
Sociodemographics, insurance, neighborhood deprivation index, health literacy, comorbidities	Baseline	Survey
Financial worry  and health-related social risks 	Baseline & 6mo	Survey

- Any mention of ER is only for UCI Health patients.

## 9. SAFETY AND TREATMENT-EMERGENT ADVERSE EVENT REPORTING

We do not anticipate any adverse events related to participation in this study beyond usual care.

If a participant report feeling distressed as a result of study participation, they may choose not to continue or to complete them and/or speak with the research team.

### 9.1. Reporting Protocol Violations and Protocol Deviations

Protocol Violation are defined as an accidental or unintentional change to or noncompliance with the IRB-approved protocol that increases risk or decreases benefit

and/or affects the subject's rights, safety, welfare, and/or the integrity of the data. Examples of incidents that may be considered violations include: enrolling a participant who does not meet the inclusion criteria; obtaining verbal consent before the initiation of study procedures when the IRB requires signed, written informed consent. [Reference: Policy #57 UCI HRPP Policy and Procedure Glossary].

Protocol Deviations are defined as an accidental or unintentional change to the research protocol that does not increase risk or decrease benefit or have a significant effect on the participant's rights, safety or welfare, or on the integrity of the data. Deviations may result from the action of the participant, researcher, or staff. Examples: a rescheduled study visit, or failure to collect an ancillary self-report questionnaire data (e.g., quality of life) see Policy #57 UCI HRPP Policy and Procedure Glossary (<https://www.research.uci.edu/compliance/human-research-protects/hrp-policy-library/hrppPolicies.htm>).

## 9.2. Standard Reporting Requirements for Adverse Events

Adverse events, serious adverse events, deviations, violations, and unanticipated problems must be entered into the clinical trial management system, OnCore and/or Advarra EDC and must also be reported to the following entities according to the timelines mentioned in the chart below. Serious adverse events collection will start at the time patient signs consent until 30 days after the end of intervention. Adverse events will be collected from the time the research patient begins treatment until 30 days after the end of intervention. All adverse events/serious adverse events should be followed until resolution or stabilization, or the subject dies or withdraws consent from participation in the study. [Table 3](#) lists the various reporting schedules for AEs by event type.

**Table 3 Standard Reporting Requirements for Adverse Events by Event Type**

Event Type	Coordinating Center/Principal Investigator	UCI IRB	CFCCC DSMB
Unanticipated Problem	Within 24 hours from date the site is aware of the event, the site should enter this information into OnCore and/or Advarra EDC.	Within 5 business days submit a report within KR Protocols .	Within 5 days from date PI is aware of the event. This information must be reported into OnCore and/or Advarra EDC.
AEs and SAEs (non-Unanticipated Problem)	Please refer to section 7.5 for reporting timeframes on AEs and SAEs.	N/A	Please refer to section 7.5 for clarification

Event Type	Coordinating Center/Principal Investigator	UCI IRB	CFCCC DSMB
			on reporting timeframes for AEs and SAEs.
Noncompliance	N/A	N/A	Please refer to section 7.5 for reportable deviations or violations.
Serious or continuing noncompliance	Within 24 hours via email	Within 5 business days submit a report in Kuali Protocols .	Within 5 days from date PI is aware of the event.
Prospective/Planned Deviations	At least 5 business days prior to the event via email	At least 48 hours prior to date the request is needed by. Submit a Prospective Deviation Request within Kuali Protocols .	At the time of progress review as aggregate reports

### Adverse Event/Serious Adverse Events

Event Type	Reporting Timeframe
Serious Adverse Events (all attributions) that meet all of the following criteria: 
 
▪ Unexpected
 
▪ Grades 3-5
 
▪ Occurring during treatment or within 30 days of the end of treatment*
 
	5 business days from date the PI is aware of the event
Adverse Events that meet all of the following criteria: 
 
▪ Unexpected
 
▪ Study related (possibly, probably, or definitely)
 
▪ Grades 3-4
 
▪ Occurring during treatment or within 30 days of the end of treatment*
 
	5 business days from date the PI is aware of the event
All other Adverse Events and Serious Adverse Events should be reported as noted in the 'Recording of Events' section	Prior to each scheduled progress review

*\* Investigators are not obligated to actively seek information regarding the occurrence of new AEs or SAEs beginning after the 30-day post-treatment period. However, if the investigator learns of such an event and that event is deemed relevant to the study, he/she should promptly document and report the event.*

## Deviations/Violations

Event Type	Reporting Timeframe
Violations as defined above (e.g. wrong dosage of drug administered, safety procedures not being conducted at specific time points)	5 business days from the date the PI is aware of the event
Deviations as defined above, including: 
 
▪ Planned deviations (e.g. rescheduling a visit that will be out of window due to a holiday)
 
▪ Unplanned deviations (e.g. rescheduled visit, a missed routine safety laboratory test for a participant with previously normal values)
 
	Prior to each scheduled progress review

## 10. STATISTICAL METHODS

### 10.1. Planned and Maximum Sample Size

A sample size of 70 patients is feasible given the limits of the study timeline and budget and will allow us to characterize key patient variables.

### 10.2. Data Analysis Plan

This is a minimal risk/Exempt study, as defined in the Chao Family Comprehensive Cancer Center (CFCCC) Data and Safety Monitoring Plan (DSMP), as shown in [Table 4](#).

**Table 4 Risk Levels as Defined in the Chao Family Comprehensive Cancer Center Data and Safety Monitoring Plan**

Risk Level	Definition	DSMB Monitoring
Level 1	
High Risk - There is the prospect of direct benefit to the subject, trial risks are high, or there is significant uncertainty about the nature or likelihood of adverse events.
 
Example: • Trials where the Principal Investigator holds the Investigational New Drug (IND) / Investigational Device Exemption (IDE). • Gene therapy, dendritic cell products from GMP suite, phase I/II development and phase I studies, first in human, etc.
	Every two months after subject enrollment

Level 2	
Medium Risk - Trials where risks are recognized as being greater than low risk, but are not considered high. There is a medium to high probability of a moderate-severity event occurring as a result of trial participation.
 
Example: • FDA exempt IND/IDE trials of any phase.
	Every six months after subject enrollment
Level 3	
Low Risk – Trials that are greater than minimal risk (45 CFR 46.102 (j)). There is a moderate probability (25-50%) of the occurrence of a low-severity event (grade 1 and 2) that is completely reversible or the likelihood of serious harm occurring is low.
 
Example: • Trials that may include interventions or invasive procedures that present low risks, reasonably commensurate with those expected in medical or dental practice, but do not fit in an IRB-expedited review category • Post-marketing studies (e.g. Phase IV drug/device study (as defined by FDA) previously determined to be low risk).
	Every twelve months after subject enrollment
Level 4	
Exempt – Trials that are industry-sponsored, NCTN-sponsored, and/or trials monitored by an external DSMB. Also includes trials that are IRB-exempt and IRB-expedited protocols (determined by the IRB as minimal risk).
 
Minimal risk means that the probability and magnitude of harm or discomfort anticipated in the research are not greater in and of themselves than those ordinarily encountered in daily life or during the performance of routine physical or psychological examinations or tests. (45 CFR 46.102 (j))
 
Example: • Trials that qualify under IRB expedited categories 2-7 and category 13. • Trials that are IRB-exempt, and non-interventional/non-therapeutic trials.
	N/A

### **10.3. Safety and Tolerability Analyses**

Not applicable

### **10.4. Statistical Analyses**

We will work with the Biostatistical Shared Resource, and report proportion of LDCT order, receipt of LDCT, and LCS discussion using descriptive measures. We will compare pre-post measures of perceived risk to lung cancer, LCS benefits, barriers, and self-efficacy using paired t-tests or Chi-squared tests, where appropriate. Multivariable regression analyses will be performed adjusting for covariates. We will report rate concordance of EMR and self-reported smoking history. Qualitative interviews will be translated and transcribed verbatim, and they will be reviewed and discussed iteratively using a “theoretically-driven thematic analysis” approach. The coding sequence will be conducted on a line-by-line unit of analysis using the Dedoose online system. We will use deductive and inductive approaches, organizing the data according to the domains in the interview guide and then open code the transcripts and inductively search for specific patterns and themes in each domain. We will develop the codebook based on the domains, emergent themes, and discussion. Coders will independently (and then collectively) examine and assemble coded data to identify themes within categories and relationships among them.

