Study Intervention	Our proposed intervention, informed by the Health Belief Model  , is a multi-level intervention including: (1) PCP notifications of patients' LCS eligibility (addressing provider time constraints and barrier in identifying eligible patients); (2) patients' education (addressing knowledge barriers); (3) patients' referral to financial navigation resources (addressing health-related social risks); and (4) patients' reminder to discuss LCS during PCP visit.
Baseline Assessments	Baseline survey at enrollment
Efficacy Assessments	Follow-up survey 6 months after enrollment
Statistical Methodology	Descriptive measures, comparison of pre- and post- intervention endpoints
Efficacy Endpoints	Primary end point is order of LDCT within 6 months after enrollment assessed with self-reported surveys (for UCI and non-UCI Health patients) and EMR data extraction (for UCI Health patients)

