##### 5.2. Overall Study Design

We will conduct a single arm longitudinal clinical trial of 70 LCS-eligible patients with a PCP appointment at UCI health within five **months** after enrollment. All patients will complete a baseline survey to assess their perceptions and barriers towards LCS and will receive a multi-level intervention. All patients will complete a survey at 6 months post-enrollment to assess changes in perceptions and knowledge, receipt of an order for LDCT or completion of LDCT, and experience with intervention. All primary care providers of enrolled patients will be sent a survey 3 months after last patient enrollment to assess providers' barriers to order LCS. We will interview randomly selected up to 15 patients and 5 PCP participants with highest enrolled patients in the study, who consent to be interviewed to assess experience with the intervention.

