#### 7.5. Baseline Survey

Patients will be asked to complete a 15-min survey either on the phone or online via REDCap based on preference. This survey includes validated measures utilizing the Health Belief Model to assess perceived risk of getting lung cancer, benefits and barriers to LCS, and self-efficacy for LCS, prior receipt of any screening exam, overall willingness to undergo LCS with LDCT, and engage in receiving LCS educational information. We will further screen for health-related social risks such as financial hardship, difficulties in paying for food, transportation, and housing instability as a barrier to receipt of LCS, and query on demographics, insurance, health literacy, zip code (to assess neighborhood socioeconomic status), and presence of other comorbidities and healthy behaviors. Participants with completed survey will be sent a \$15 gift card. Survey materials will be available in English, Spanish, and Vietnamese.

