## 7.7. Patient Follow-up

Patients will be surveyed 6 months after enrollment to assess self-reported LCS discussion with PCP, provider order of LDCT, and patients' receipt of LDCT. We will also extract these from EMR only for UC-Health patients. Patients will be queried on LCS perceived risks, benefits, barriers, and self-efficacy, experience with intervention including educational material, reminders, and self-referral to PAF if PAF brochure was received.

Surveys will be completed online (REDCap), on the phone or paper (mailed with a pre-stamped pre-addressed envelope) based on patient's preference. Patients with completed survey will receive a \$15 gift card.

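### Section 10.4 offers only chi-squared tests for pre-post belief measures analysed as categories, which ignores the pairing within patients and can miss real change

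*Combined protocol and SAP*

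**What the plan says.** The Statistical Methodology row of the synopsis (section 1) reads "Descriptive measures, comparison of pre- and post- intervention endpoints". Section 10.4 gives the detail for the belief measures: "We will compare pre-post measures of perceived risk to lung cancer, LCS benefits, barriers, and self-efficacy using paired t-tests or Chi-squared tests, where appropriate". It then adds a multivariable regression adjusted for covariates and says nothing about repeated measurements on a patient.

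The measures are taken twice on the same people. Of the baseline questionnaire, section 7.5 says "This survey includes validated measures utilizing the Health Belief Model". Of the 6-month questionnaire, section 7.7 says "Patients will be queried on LCS perceived risks, benefits, barriers, and self-efficacy". Table 2 lists the row "Pt perceived risks, benefit, barriers, and self-efficacy using LCS health belief mode" among the efficacy outcomes, at baseline and 6 months. Section 5.2 describes a single-arm longitudinal study of 70 patients and adds: "All patients will complete a survey at 6 months post-enrollment to assess changes in perceptions and knowledge".

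The documents name no McNemar, Bowker, Stuart-Maxwell or Wilcoxon signed-rank test, no GEE and no mixed model. They do not say which belief measures, if any, would be analysed as categories.

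**The concern.** The design gives each patient a before and an after answer. The plan respects this for continuous measures through the paired t-test. For everything else the only method it names is the chi-squared test, and neither ordinary way of running that test answers the question:

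- **Baseline proportion against 6-month proportion.** This counts each patient twice, as a member of two independent groups. The standard error leaves out the within-patient covariance and is too large when answers correlate positively, which is usual when one person answers the same belief item twice.
- **Baseline answer cross-tabulated against 6-month answer.** This tests whether the two answers are associated, not whether they changed.

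The belief measures are efficacy outcomes, and the pre-post comparison is the only comparison the synopsis names. Section 10.1 justifies the sample of 70 by timeline and budget, so there is little power to spare. An item wrongly reported as showing no clear change, or an interval computed as if the surveys were independent, would also mislead anyone using this pilot to plan a later study.

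**Working it through.** **Inputs from the documents.** n = 70 patients (sections 5.2, 5.4, 10.1), measured at baseline and 6 months (sections 7.5, 7.7, Table 2), with the tests named in section 10.4. The documents give no alpha, effect size, correlation or power for this comparison, so there is no stated figure to reproduce.

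**Assumptions.** Two-sided alpha 0.05; a binary item with proportions p1 at baseline and p2 at 6 months; within-patient correlation ρ of 0, 0.3, 0.5 or 0.7; 70 pairs, or 56 pairs (80% follow-up, 0.8 × 70).

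**Step 1: standard errors.** Write q = 1 − p.

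- Paired variance of the difference: [p1q1 + p2q2 − 2ρ√(p1q1p2q2)]/n.
- With the surveys treated as independent, the third term is dropped.

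For 50% to 65%, ρ = 0.5, n = 70: p1q1 = 0.25, p2q2 = 0.2275, √(0.25 × 0.2275) = 0.2385.

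- Paired SE = √[(0.4775 − 0.2385)/70] = 0.058.
- Independent SE = √(0.4775/70) = 0.083.

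**Step 2: true type I error of the unpaired test.** With no change, its z statistic has variance of about 1 − ρ, so the actual two-sided error is about 2[1 − Φ(1.96/√(1 − ρ))]. For ρ = 0 / 0.3 / 0.5 / 0.7 this gives 5.0 / 1.9 / 0.6 / 0.03%. Simulation with 70 pairs and 50% at both times agrees: 5.1 / 2.0 / 0.6 / 0.04%. McNemar mid-p gives 4.7 / 4.5 / 4.7 / 4.2%, and exact McNemar 3.3 / 3.0 / 2.9 / 2.3%.

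**Step 3: power by simulation.** Paired multinomial samples with p11 = p1p2 + ρ√(p1q1p2q2), 400,000 replicates per setting; chi-squared without continuity correction.

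| Setting | Test | ρ = 0 | 0.3 | 0.5 | 0.7 |
|---|---|---|---|---|---|
| 70 pairs, 50% to 65% | chi-squared | 44% | 42% | 41% | 37% |
| | McNemar mid-p | 42% | 55% | 72% | 95% |
| | McNemar exact | 36% | 48% | 64% | 90% |
| 56 pairs, 50% to 65% | chi-squared | 35% | 32% | 30% | 24% |
| | McNemar mid-p | 34% | 46% | 61% | 87% |
| 70 pairs, 50% to 60% | chi-squared | 22% | 18% | 14% | 8% |
| | McNemar mid-p | 21% | 27% | 37% | 57% |

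The 0.7 column for 50% to 65% is extreme. The largest possible correlation there is (0.5 − 0.325)/0.2385 = 0.73, and at 0.7 only 0.8% of patients move from yes to no. The 0.3 and 0.5 columns are the ones to rely on. A separate run with 40% to 55%, 70 pairs and ρ = 0.5 gave 40% for chi-squared and 72% for asymptotic McNemar.

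**Step 4: worked example.** Of 70 patients, 32 say yes twice, 22 no twice, 13 change to yes and 3 change to no. Yes answers go from 35 to 45, a difference of 10/70 = 14.3 points; the within-patient correlation is 0.57.

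- Unpaired chi-squared = 2.917, p = 0.088. Independent 95% CI: 0.143 ± 1.96 × √(0.5 × 0.5/70 + 0.643 × 0.357/70), or −1.9 to 30.5 points.
- Asymptotic McNemar = (13 − 3)²/(13 + 3) = 6.25, p = 0.012; exact p = 0.021; mid-p = 0.013. Paired 95% CI: 0.143 ± 1.96 × √(16 − 10²/70)/70, or 3.6 to 25.0 points.

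**Step 5: the cross-table reading.** Take 28 yes-yes, 7 yes-no, 7 no-yes and 28 no-no: 35 of 70 say yes each time, so there is no net change. Chi-squared on this table is 70 × [(28 × 28 − 7 × 7)/(35 × 35)]² = 70 × 0.36 = 25.2, p = 0.0000005. The test rejects strongly although nothing has changed.

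**The case against.** The best defence is that the sentence is loose rather than wrong. It opens by calling the measures pre-post, it already pairs the t-test, McNemar's statistic is itself a chi-squared statistic, and the authors will work with a biostatistics group. McNemar's test may therefore be what they meant. That possibility stands, but the text does not say it: "using paired t-tests or Chi-squared tests, where appropriate" leaves a choice between two listed tests, and neither is a named paired categorical test.

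Second, no categorical belief measure is identified. The four constructs match a single Table 2 row that cites published Health Belief Scales. If all four are scored as scales, the paired t-test covers them and the chi-squared option is never used. This also stands, and makes the practical effect conditional. The plan does, however, list a categorical option for exactly these measures.

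Third, every power figure rests on assumed inputs, the highest correlation lies close to its mathematical limit, and the worked example was chosen so that the two p-values fall on either side of 0.05. All true; the conclusion needs only a moderate positive correlation.

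Fourth, the consequence is limited. This is a feasibility study, the LDCT order endpoint is descriptive, section 10.4 plans no confidence interval for these comparisons, and on the main reading the error is conservative. That bounds the importance of the point without making the named test suitable.

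**Conclusion.** The concern holds. As written, any belief measure analysed as a category would be compared with a test that either ignores the pairing or tests something other than change. Under the assumptions above (binary item, 50% to 65%, alpha 0.05, 70 pairs), using chi-squared instead of McNemar mid-p costs about 13 points of power at correlation 0.3 (55 − 42) and 31 points at 0.5 (72 − 41). At zero correlation nothing is lost. On this reading the unpaired test does not inflate false positives.

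The point is confined to measures analysed as categories. Scale scores compared by paired t-test and the primary endpoint are unaffected. It should be corrected, with medium confidence about its practical effect, because the documents do not show which measures would take the categorical route.

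**What to change.** In section 10.4, replace the chi-squared option with wording such as: McNemar's test (mid-p) for binary items and the Wilcoxon signed-rank test for ordinal items, with the Stuart-Maxwell test for any unordered item with more than two categories, each reported with the paired difference and its 95% confidence interval where applicable. State which belief measures are analysed as scale scores and which as categories. If a regression includes both time points, account for clustering by patient with GEE or a mixed model. If McNemar's test was intended all along, naming it settles the main point.

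The cost is a sentence or two. No new data are needed, since the paired t-tests already require the two surveys to be linked by patient. The one statistical price is small: the exact McNemar test is conservative (type I error 2.3 to 3.3% in the settings above) and gives up about 7 points of power at zero correlation, while the mid-p version stays at 4.2 to 4.7% and gives up about 1 point.

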## **11. STUDY MANAGEMENT**

### **11.1. Conflict of Interest**

Any investigator who has a conflict of interest with this study (patent ownership, royalties, or financial gain greater than the minimum allowable by their institution, etc.) must have the conflict reviewed by their own institution’s Conflict of Interest (COI) Committee, with documentation of this process maintained in the study file.

### **11.2. Institutional Review Board (IRB) Approval and Informed Consent**

It is expected that the IRB will have the proper representation and function in accordance with federally mandated regulations.

The Institutional Review Board (IRB) must review the protocol and the related Informed Consent Form (ICF) prior to study initiation and provide signed and dated documentation of their approval. The IRB must also approve any protocol or ICF amendments prior to their implementation, again providing signed and dated proof of approval.

In obtaining and documenting informed consent, the investigator should comply with the applicable regulatory requirement(s), and should adhere to Good Clinical Practice (GCP) and to ethical principles that have their origin in the Declaration of Helsinki.

Before recruitment and enrollment onto this study, the patient will be given a full explanation of the study and will be given the opportunity to review the consent form. Each consent form must include all the relevant elements currently required by the FDA

Regulations and local or state regulations. Once this essential information has been provided to the patient and the investigator is assured that the patient understands the implications of participating in the study, the patient will be asked to give consent to participate in the study by signing an IRB-approved consent form.

Prior to a patient's participation in the trial, the written informed consent form should be signed and personally dated by the patient and by the person who conducted the informed consent discussion.

